#### V- Comparison between the two groups regarding niche characteristics

[figure not shown]
Length in group I ranged from 0.3-1.1 with mean value  $0.707\pm0.23$  and in group II ranged from 0.32-1.4 with mean value  $0.570\pm0.21$ . Width in group I ranged from 0.35-1.3 with mean value  $0.737\pm0.26$  and in group II ranged from 0.4-1.12 with mean value  $0.640\pm0.19$ . There was statistical significant increase in group I than group II regarding length and width (P=0.010, 0.046). There were no statistical significant differences between the two studied groups regarding depth, AMT and RMT (P= 0.421, 0.441, 0.378). (Table 5, Fig. 18)

Table (5): Comparison between the two studied groups regarding niche characteristics.

Niche characteristics	Group I	Group II	T test P value
Length (cm)			
Range	0.3-1.1	0.32-1.4	0.010+
Mean	0.707	0.570	0.010*
SD	0.23	0.21	
Width (cm)			
Range	0.35-1.3	0.4-1.12	0.046*
Mean	0.737	0.640	0.040*
SD	0.26	0.19	
Depth (cm)			
Range	0.21-0.80	0.20-0.49	0.421
Mean	0.331	0.317	0.421
SD	0.15	0.09	
AMT			
Range	0.85-1.6	0.92-1.39	0.441
Mean	1.109	1.115	0.441
SD	0.16	0.14	
RMT			
Range	0.24-1.4	0.34-0.92	0.378
Mean	0.716	0.701	0.376
SD	0.21	0.15	

Group I. cesarean section with bladder dissection Group II: cesarean section without bladder dissection t-test = student t-test p was significant if  $\leq 0.05$  \* = Significant at level 0.05

[figure not shown]

Figure (18): Comparison between the two studied groups regarding niche characteristics.

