## IV-Comparison between two groups as regard incidence of niche

Niche is defined as an anechoic space at least 2 mm depth at the presumed site of the caesarean section scar.

The incidence of niche was higher in group I, yet it did not reach statistical significance. (P=0.087). (Table 4, Fig. 17)

Table (4): Comparison between the two studied groups regarding incidence of niche

Incidence of niche	Group I		Group II		
	No %		No	%	
Absent	89	71.2	99	79.2	
Present	35	28.0	26	20.8	
X 	1.94				
P value	0.087				

Group I. cesarean section with bladder dissection Group II: cesarean section without bladder dissection  $X^2$  = Chi square-test p was significant if  $\leq 0.05$ 

[figure not shown]

Figure (17): Comparison between the two studied groups regarding incidence of niche

[figure not shown]

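### Table 5 prints P values that its stated Student's t-test does not give two-sided, marks width as significant when it is not, and summarises skewed depth by mean and SD only

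*SAP*

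**What the plan says.** Table 5 gives range, mean, SD and one P value for niche length, width, depth, AMT and RMT. It gives no n, median, IQR, confidence interval or check of the distributions. Its footnote names the test: "t-test = student t-test p was significant if" at most 0.05. It does not say whether the test is one- or two-sided. The protocol's Results section promises only standard statistical methods.

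The text of section V draws two conclusions:
- "There was statistical significant increase in group I than group II regarding length and width (P=0.010, 0.046").
- "no statistical significant differences between the two studied groups regarding depth, AMT and RMT (P= 0.421, 0.441, 0.378").

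Two other statements matter here. Section IV sets a floor on depth: "Niche is defined as an anechoic space at least 2 mm depth". Section V gives length in group II this way: "and in group II ranged from 0.32-1.4 with mean value" 0.570 and SD 0.21. The longest niche in group I is 1.1 cm.

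**The concern.** A reader can test Table 5 against itself, because mean, SD and (through Table 4) n are enough to recompute a Student's t-test. If the printed P values do not come back, the two starred differences are in doubt. They are the only differences in the table called significant, and both put the larger niche in the bladder-dissection group.

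The ranges also suggest that mean and SD describe some columns poorly. Depth has a hard lower limit and a long upper tail in group I. In group II length, one value lies far from the rest and exceeds every niche in the group with the larger mean. That could be a real finding, a recording error, or two ranges printed under the wrong arm.

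**Working it through.** **Inputs.** Means, SDs and ranges are from Table 5. Table 5 gives no n, so I assume the women with a niche in Table 4: 35 in group I and 26 in group II ("Present 35 28.0 26 20.8"). In that table 89 + 35 = 124 in group I, one short of 125, so I also tried 36.

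**Test.** Pooled SD sp = √{[(n₁−1)s₁² + (n₂−1)s₂²]/(n₁+n₂−2)}; SE = sp·√(1/n₁ + 1/n₂); t = difference/SE on 59 df.

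Length: sp = √[(34×0.23² + 25×0.21²)/59] = 0.222; SE = 0.222×√(1/35 + 1/26) = 0.0574; t = 0.137/0.0574 = 2.39. Two-sided P = 0.020 and one-sided P = 0.010. The printed 0.010 is therefore reproduced, but only as a one-sided value.

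The same steps for all five dimensions:

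| Dimension | Difference, I − II (95% CI) | t | Two-sided P | One-sided P | Printed P |
|---|---|---|---|---|---|
| Length | 0.137 (0.022 to 0.252) | 2.39 | 0.020 | 0.010 | 0.010* |
| Width | 0.097 (−0.024 to 0.218) | 1.61 | 0.113 | 0.057 | 0.046* |
| Depth | 0.014 (−0.052 to 0.080) | 0.422 | 0.67 | 0.34 | 0.421 |
| AMT | −0.006 (−0.085 to 0.073) | −0.15 | 0.88 | 0.440 | 0.441 |
| RMT | 0.015 (−0.082 to 0.112) | 0.31 | 0.76 | 0.379 | 0.378 |

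**Could rounding, n or unequal variances explain the gaps?** I varied every mean and SD over its rounding limits, with n₁ = 35 or 36.
- Width: two-sided P is 0.101 to 0.124 pooled and 0.085 to 0.108 by Welch's test. One-sided it is 0.050 to 0.062 pooled. Only a one-sided Welch test (0.042 to 0.054) reaches the printed 0.046.
- Depth: two-sided P is 0.64 to 0.71 and one-sided 0.32 to 0.35 (pooled). Welch's test does not reach 0.421 either (0.61 to 0.69 two-sided, 0.31 to 0.34 one-sided). The t statistic, 0.422, almost equals the printed P.

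**Shape of depth.** Section IV allows no depth below 0.20 cm, and the ranges are "0.21-0.80 0.20-0.49". In group I the minimum is (0.331 − 0.21)/0.15 = 0.8 SD below the mean and the maximum is (0.80 − 0.331)/0.15 = 3.1 SD above it. Mean minus one SD is 0.18 cm, which by definition is not a niche.

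**The 1.4 cm length.** (1.4 − 0.570)/0.21 = 3.95 SD; the two-sided 5% Grubbs limit for n = 26 is 2.84. It can be only one woman. Two such values need a sum of squares of at least 2×0.83² + (2×0.83)²/24 = 1.49, and the SD allows at most 25×0.215² = 1.16.

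Without her:
- mean = (26×0.570 − 1.4)/25 = 0.537
- sum of squares = 25×0.21² − 26×0.83²/25 = 1.1025 − 0.7165 = 0.386
- SD = √(0.386/24) = 0.127
- difference = 0.707 − 0.537 = 0.170; t = 3.35; two-sided P = 0.0014 (0.0010 to 0.0020 over rounding)

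**Group I maxima.** Depth 0.80, AMT 1.6 and RMT 1.4 lie 3.1, 3.1 and 3.3 SD above their means (Grubbs limit 2.98 for n = 35). Removing one such value takes the depth difference from 0.014 to 0.0002 (−0.0010 to 0.0014 over rounding; P = 0.99). It takes the RMT difference from 0.015 to −0.005 (P = 0.91).

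**The case against.** The strongest defence is that a t-test on 35 v 26 women is a standard method and copes with skewness of this degree. That stands. I simulated depth as a shifted gamma variable with floor 0.20 and mean 0.331 in both arms (10,000 runs). The pooled t-test rejected in 4.7% of runs with both SDs at 0.15, and in 4.7% with the printed SDs of 0.15 and 0.09. With those unequal SDs and equal means, Mann-Whitney rejected in about 20%, because it then answers a different question. Replacing every t-test by a rank test is therefore not clearly an improvement.

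A reader might also infer three stronger things that the documents do not support.

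- *That the length finding hangs on one woman.* Removing her strengthens it, and removing any other single group extreme leaves two-sided P between 0.011 and 0.032.
- *That the direction of the depth and RMT differences hangs on one woman.* Depth falls to about zero with no reversal shown. RMT does change sign, but section V reports both as non-significant, so no stated conclusion changes. Up to three women could share each of those maxima.
- *That all five dimensions are cut off at 2 mm.* The definition limits depth only.

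The Grubbs evidence for depth, AMT and RMT is also modest: with ten columns examined, only the length value is beyond reasonable doubt. None of this touches the mismatch in P values.

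**Conclusion.** The point holds as a reporting and analysis error in Table 5. Four of the five printed P values are either undeclared one-sided values (length, AMT, RMT) or not obtainable from the stated test (depth). The fifth, width, is starred at 0.046 but is 0.11 two-sided, so its significance is not supported. Length remains significant at 0.020, twice the printed value.

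Mean and SD alone misdescribe depth. The length difference lies between 0.137 and 0.170 cm depending on whether one unverified value is kept. The depth and RMT differences are near zero with or without their maxima.

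This rests on n = 35 v 26; using 36 in group I changes nothing material. That the depth t statistic was printed as its P value is a plausible explanation, not an established one. A rank test cannot be computed from the published summaries.

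**What to change.** 1. State n for each column of Table 5.
2. Check the 1.4 cm length in group II, and the group I maxima for depth (0.80), AMT (1.6) and RMT (1.4), against the scan records. Check also whether the two length ranges were exchanged between the arms.
3. Recompute all five P values two-sided, say so in the footnote, and give each mean difference with its 95% CI.
4. Replace the printed depth P. If the recomputation confirms it, remove the star and the significance claim for width, and rewrite the text of section V to match.
5. Add median (IQR) and a two-sided Mann-Whitney test for each dimension as a sensitivity analysis beside the t-test, not in place of it.

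The cost is five comparisons rerun on data already held and four values checked, with no new patients or procedures. The downside for the authors is that width is no longer a positive finding and the length P value becomes less striking.

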### II-Comparison between two groups as regard obstetric history

Gravidity in group I had mean value  $1.44\pm1.03$  and in group II had mean value  $1.312\pm0.737$ . Parity in group I had mean value  $0.136\pm0.68$  and in group II had mean value  $0.192\pm0.73$ . It was found that most of cases had no abortion in two studied groups 97(77.6%) and 99(79.2%) respectively. No ectopic cases was higher with 125(100%) and 124(99.2%) respectively. Gestational age had mean value  $37.41\pm2.37$  and in group II had mean value  $36.99\pm2.50$ .

[figure not shown]
There were no statistically significant differences between the two studied groups regarding gravidity (P = 0.133), parity (P = 0.069), abortion (P=0.465), ectopic (P=0.159) and gestational age (P = 0.175). (Table 2, Fig. 15)

[figure not shown]
Obstetric history	Group I	Group II	T test P value
Gravidity			
Range	1-9	1-6	0.133
Mean	1.44	1.312	0.155
SD	1.03	0.77	
Parity			
Range	0-6	0-4	0.069
Mean	0.142	0.192	0.009
SD	0.68	0.73	
Abortion			
No	97 (77.6%)	99 (79.2%)	0.465
1-2	27 (21.6%)	23 (18.4%)	0.403
>2	1 (0.8%)	3 (2.4%)	
Ectopic			
No	125(100.0%)	124 (99.2%)	0.159
Yes	0.0 (0.0%)	1 (0.8%)	
Gestational age			0.175

[figure not shown]
Table (2): Comparison between the two studied groups regarding obstetric history.

Range	34-41	33-41	
Mean	37.41	36.99	
SD	2.37	2.50	

Group I. cesarean section with bladder dissectiont-test = student t-testGroup II: cesarean section without bladder dissection p was significant if  $\leq 0.05$ 

[figure not shown]

Figure (15): Comparison between the two studied groups regarding obstetric history.

[figure not shown]

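### Table 5 calls niche width significantly larger with bladder dissection (P=0.046), but the printed means and SDs give a two-sided P of about 0.10 to 0.11

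*SAP*

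**What the plan says.** SAP section V compares five niche measurements between group I (bladder dissection) and group II (no dissection). Its conclusion on two of them is "There was statistical significant increase in group I than group II regarding length and width (P=0.010, 0.046"). For the other three it states "There were no statistical significant differences between the two studied groups regarding depth, AMT and RMT (P= 0.421, 0.441, 0.378").

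For width, Table 5 prints mean 0.737, SD 0.26 cm in group I and mean 0.640, SD 0.19 cm in group II. The footnote reads "t-test = student t-test p was significant if" at or below 0.05, and the asterisk is defined as "Significant at level 0.05".

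Table 5 prints no n. The nearest source is Table 4 in section IV, whose niche row reads "Present 35 28.0 26 20.8", that is, 35 women in group I and 26 in group II. Neither document says whether tests are one-sided or two-sided. The protocol's Results section refers only to standard statistical methods.

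**The concern.** A mean difference of 0.097 cm with SDs of 0.26 and 0.19 is not large for groups of about 35 and 26, and a two-sided P below 0.05 looks too small for it. Length and width are the only niche measurements declared significant. If the width result does not follow from the printed figures and the named test, a reader would wrongly conclude that dissection has been shown to produce wider niches. If the cause is undeclared one-tailed P values, the other rows of the table are affected too.

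**Working it through.** **Inputs.** Means and SDs are from Table 5. The group sizes n1=35 and n2=26 are assumed from Table 4. Group I in Table 4 sums to 89+35=124, not 125, so n1=36 was also tried.

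**Width, Student t-test (the named test).**
- Pooled variance = (34×0.26² + 25×0.19²)/59 = (2.2984 + 0.9025)/59 = 0.05425, so the pooled SD is 0.2329.
- SE = 0.2329 × √(1/35 + 1/26) = 0.2329 × 0.2589 = 0.0603.
- t = (0.737 − 0.640)/0.0603 = 0.097/0.0603 = 1.608, df 59.
- Two-sided P = 0.113; one-tailed P = 0.0565.
- 95% CI = 0.097 ± 2.001×0.0603 = -0.024 to 0.218 cm.

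**Width, Welch t-test.**
- SE = √(0.26²/35 + 0.19²/26) = √(0.001931 + 0.001388) = 0.0576.
- t = 0.097/0.0576 = 1.683, df 59.0.
- Two-sided P = 0.098; one-tailed P = 0.0488.
- 95% CI -0.018 to 0.212 cm.

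The printed 0.046 is not reproduced by the named test with either sidedness.

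**Sensitivity.** The means were varied by ±0.0005 and the SDs by ±0.005, with n1 of 35 or 36:

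| Test | Two-sided P | One-tailed P |
|---|---|---|
| Student | 0.101 to 0.124 | 0.0504 to 0.062 |
| Welch | 0.085 to 0.108 | 0.042 to 0.054 |

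Using the whole randomized groups (125 v 125) gives P=0.0009, so that does not explain 0.046 either. At 35 v 26, a two-sided P of 0.05 needs a difference of 2.001×0.0603 = 0.121 cm. With the printed difference it needs both groups to be about 1.53 times larger, roughly 54 v 40 women.

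**The five rows together (Student, 35 v 26).**

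| Measurement | t | Two-sided P | One-tailed P | Printed P |
|---|---|---|---|---|
| Length | 2.386 | 0.020 | 0.0101 | 0.010 |
| Width | 1.608 | 0.113 | 0.0565 | 0.046 |
| Depth | 0.422 | 0.674 | 0.337 | 0.421 |
| AMT | -0.153 | 0.879 | 0.440 | 0.441 |
| RMT | 0.310 | 0.758 | 0.379 | 0.378 |

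Length, AMT and RMT agree with the one-tailed value to within rounding of the inputs. This also supports 35 v 26 as the group sizes. Depth agrees with neither form; over input rounding its one-tailed P runs from 0.319 to 0.354. For length the difference is 0.137 cm, 95% CI 0.022 to 0.252.

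**Sidedness elsewhere.** Section II reports no significant differences "regarding gravidity (P = 0.133), parity (P = 0.069), abortion (P=0.465), ectopic (P=0.159) and gestational age (P = 0.175"). With 125 per group and the Table 2 SDs, gravidity gives t=1.113 and a two-sided P of 0.267; half of that is the printed 0.133. Gestational age gives t=1.363 and a two-sided P of 0.174, which matches the printed 0.175 without halving. The document is therefore not consistent.

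**The case against.** The strongest reply is that 0.046 can be reached. A one-sided Welch test gives 0.0488, and its rounding range (0.042 to 0.054) includes 0.046. That stands as a possible explanation of how the number arose. It does not support the claim: the footnote names the Student test, no one-sided hypothesis is declared in either document, and a reader will take significance at 0.05 as two-sided.

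The group sizes are also assumed. Table 5 gives no n and does not say whether it shows the 3-month or the 6-month scan in the protocol. This stands as a caveat, so recomputed P values are expected values until the raw data are used. Three of the other rows fit 35 v 26, however, and the sizes needed to rescue width are well above the Table 4 counts.

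Finally, the consequence is limited. Width is not among the protocol's four outcome measures, and the comparison is a descriptive one among women with a niche. Niche incidence, depth, AMT and RMT are all reported as non-significant already. This is correct and bounds the importance of the error, but the printed statement about width remains unsupported.

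**Conclusion.** The concern holds. From the printed means and SDs and the Table 4 niche counts, the two-sided P for width is 0.113 (Student) or 0.098 (Welch), against a printed 0.046. The stated conclusion changes from significant to not significant, and input rounding or a group I count of 36 does not alter that. The result rests on one assumption, that Table 5 covers the 35 and 26 women with a niche.

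Undeclared one-tailed P values are a likely cause but are not proven, because depth fits neither form and the named test does not give 0.046 even one-tailed. For length the printed P is half the two-sided value, but its significance survives at about 0.020. The result for niche incidence is not affected by this point.

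**What to change.** - Re-run the five Table 5 tests two-sided from the raw data and replace the printed P values. If 35 v 26 is right and the printed means and SDs are correct, the Student values should be about 0.020 (length), 0.11 (width), 0.67 (depth), 0.88 (AMT) and 0.76 (RMT). Depth needs particular attention, since its printed P has no explanation.
- Unless the raw data show otherwise, delete the asterisk on width and take width out of the significance sentence.
- State n per group, the sidedness and the t-test variant under the table, and label it as a comparison among women with a niche. Mean differences with 95% CIs would be a useful addition.

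The cost is five t-tests, one reworded sentence and one revised table, with probably one fewer significant result.

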## **AIM OF THE WORK**

The aim of this study is to compare Incidence of cesarean scar defect in cases of cesarean section with and without bladder flap dissection.

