## **Outcome measures:**

- 1. Incidence of occurrence of cesarean scar (cs) niche in each group.
- 2. Correlation between the depth of niche and the residual myometrium in each group.
- 3. Comparison between the thicknesses of residual myometrium to adjacent normal myometrium in each group.
- 4. Complains of niche if present.

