# **RESULTS**

The results will be tabulated and statistically analyzed, using the standard statistical methods.

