# Figure (19): Post delivery complain in the two studied groups

# VII- Comparison between the two groups regarding incidence of postdelivery complaint and the type of contraceptive used

It was found that the highest incidence of complaint in both groups was found in cases with no contraceptive, followed by IUD user. There was statistical significant difference between two studied groups regarding complaint incidence in non contraceptive-user (P=0.036) (Table 7, Fig. 20)

Table (7): Relation between the incidence of post delivery complication and the type of contraceptive used.

		up I 13″		Group II P va "n=8"	
	No	%	No	%	
No	7	46.2	5	62.5	0.036*
IUD	3	23.1	2	25.0	0.521
Pops	1	7.7	0	0.0	-
COCS	1	7.7	0	0.0	-
Depoprovera	1	7.7	1	12.5	1.0

**Figure (20):** Relation between the incidence of post delivery complication and the type of contraceptive used.

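### Niche length and width are called significant although neither comparison between arms was planned; two-sided, width is not significant and length is an exploratory finding that does not support a claim of effect

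*SAP*

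**What the plan says.** The protocol's Aim of the Work is to "compare Incidence of cesarean scar defect in cases of cesarean section with and without bladder flap dissection". Its Outcome measures list has four numbered items, of which the first is "Incidence of occurrence of cesarean scar (cs) niche in each group". None is labelled primary. The other three are the correlation of niche depth with residual myometrium, residual against adjacent myometrium, and complaints. The Methods describe how length and width are measured, but no comparison of them between arms is planned. The whole analysis plan is one sentence: "The results will be tabulated and statistically analyzed, using the standard statistical methods". It names no test, sidedness, hierarchy or multiplicity rule.

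The SAP document reports seven tables. Most carry a footnote setting significance at P of 0.05 or less for each test. Table 4 (niche incidence) gives P = 0.087, and the text says this did not reach significance. Section V then says of Table 5: "There was statistical significant increase in group I than group II regarding length and width", with P = 0.010 and 0.046, and marks both "Significant at level 0.05". Two other statements of significance appear: retroverted (RVF) uterine position in section III (P = 0.03), and, in section VII, "There was statistical significant difference between two studied groups regarding complaint incidence in non contraceptive-user (P=0.036").

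**The concern.** The one question the study set out to answer has a non-significant result. All four statements of significance come from rows that are not among the listed outcomes. Two of them, length and width, describe the niche itself, so they are the ones most easily read as an effect of bladder dissection.

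Three features weaken that reading:

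- The comparisons were not planned.
- If Table 5 covers only women with a niche, the two sets compared are defined by something that happened after randomisation, so randomisation does not guarantee that they are comparable.
- Each row is tested alone at 0.05, and no document says which rows form a family.

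At stake is whether the trial is reported as having shown larger niches after dissection.

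**Working it through.** **Inputs.** Length, from Table 5: "Mean 0.707 0.570 0.010" (means in cm, then P), SD 0.23 and 0.21. Width, from Table 5: means 0.737 and 0.640, SD 0.26 and 0.19, P = 0.046. Table 5 prints no denominators. I assume the women with a niche in Table 4, "Present 35 28.0 26 20.8", that is 35 and 26.

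**Reproducing the printed length P.**
- Pooled SD = √[(34 × 0.23² + 25 × 0.21²) / 59] = 0.222
- SE = 0.2217 × √(1/35 + 1/26) = 0.0574
- t = (0.707 − 0.570) / 0.0574 = 2.386 on 59 df
- One-sided P = 0.0101, which reproduces the printed 0.010
- Two-sided P = 0.0202 (Welch 0.0188)
- 95% CI = 0.137 ± 2.001 × 0.0574 = 0.022 to 0.252 cm

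Rounding of the printed means and SDs moves the two-sided P only between 0.017 and 0.024. Table 4's group I counts sum to 124, not 125; using 36 instead of 35 gives 0.0196.

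**Other printed values that look one-sided.** AMT: printed 0.441, one-sided 0.440. RMT: printed 0.378, one-sided 0.379. Niche incidence: 35/124 v 26/125 gives a two-sided chi-square P of 0.173, half of which is 0.087, the printed figure. Depth (printed 0.421) matches neither version (0.337 one-sided, 0.674 two-sided).

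**Width.** t = 1.608, two-sided P = 0.113 (Welch 0.098). It is not significant before any correction. On its printed P, Holm over five rows gives 4 × 0.046 = 0.184.

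**Length under different families** (smallest P multiplied by the number of tests, as in Bonferroni or Holm):

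| Family | Printed P 0.010 | Two-sided P 0.0202 |
|---|---|---|
| Five Table 5 rows | 0.050 | 0.101 |
| Length, width, depth | 0.030 | 0.061 |
| Length and width | 0.020 | 0.040 |

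**The other two significant statements** (chi-square, no continuity correction).
- RVF position, 15/125 v 8/125: P = 0.126, against the printed 0.03.
- Complaints in women using no contraceptive: 7/13 v 5/8 gives P = 0.70, and 7/125 v 5/125 gives P = 0.55, against the printed 0.036.

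The tables print 23 P values (1 + 5 + 3 + 1 + 5 + 5 + 3), of which four are at or below 0.05. Recomputed two-sided, only length of those four stays below 0.05.

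**The case against.** The strongest reply is that length survives correction on the document's own figure. Holm or Bonferroni over five rows gives 5 × 0.010 = 0.050, which meets a rule of 0.05 or less. That is correct. Length fails over five rows only once the one-sided 0.010 is replaced by the two-sided 0.020. That replacement is a separate step and needs its own reason: no document states or justifies a one-sided test.

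The choice of family is also open. No document defines one, AMT and RMT are myometrial thicknesses rather than niche dimensions, and over length and width alone the two-sided value is 0.040. A reader might infer that length simply fails correction for multiplicity. The documents do not support that as a flat statement.

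A reader might also infer that testing each row at 0.05 produced all four significant statements. It did not. Width, RVF position and the contraceptive row lose significance without any correction, because their printed P values do not agree with two-sided tests on the printed data.

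Two further points stand. Naming a confirmatory outcome after its P value is printed is late, although incidence is both the sole aim and the first outcome, and its result is null, so the choice favours no positive finding. And section IV does say plainly that incidence was not significant; with no conclusions section supplied, the documents do not show the null result being displaced.

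**Conclusion.** The point holds in a limited form. The significance claim for width is unsupported: two-sided P = 0.113 uncorrected, and it fails Holm over five rows even on its printed P. Length shows a difference of 0.137 cm (95% CI 0.02 to 0.25, two-sided P = 0.020). This is nominal evidence from an unplanned comparison, and whether it survives correction depends on the family (0.101, 0.061 or 0.040). It should be reported as an exploratory difference. Calling it a significant effect goes too far, and so does calling it refuted.

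This rests on three assumptions: Table 5 uses the 35 and 26 women with a niche (36 makes no difference), the printed means and SDs are right, and tests should be two-sided because no document argues otherwise.

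**What to change.** 1. In the protocol's Outcome measures and SAP section IV, name niche incidence as the sole confirmatory outcome at two-sided 0.05, and state that it was so named after the results were known.
2. Recompute all Table 5 P values two-sided and print the denominators.
3. In section V, withdraw the significance claim for width. Report length as an exploratory, unadjusted difference with its 95% CI, without the word significant.
4. Label Tables 5 to 7 exploratory. Adding a Holm adjustment to a table so labelled is a matter of preference; if one is used, apply it to the two-sided values and state the family.
5. Recheck the P values behind the significant statements in section III (RVF position) and section VII (no contraceptive), and correct the text to match.

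This needs no new data, only recalculation and rewording. The cost is that length and width are lost as significant results; the observed differences stay on record.

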# RESULTS

This study was prospectively conducted on 250 women recruited from ElShatby university maternity hospital delivery ward; they were randomized into two groups group (A) and group (B) by closed envelop randomization.

Group (A) was undergo cesarean section with bladder dissection.

Group (B) was undergo cesarean section without bladder dissection.

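### Table 5 reports a significant arm difference in niche length and width among only the women who developed a niche, and its P values do not match a two-sided t-test; width is not significant even in that subset

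*SAP*

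**What the plan says.** The SAP document is written as a results chapter. Section IV sets the threshold: "Niche is defined as an anechoic space at least 2 mm depth at the presumed site of the caesarean section scar". Table 4 then gives the counts for groups I and II as "Present 35 28.0 26 20.8" and "Absent 89 71.2 99 79.2", and the text concludes "The incidence of niche was higher in group I, yet it did not reach statistical significance. (P=0.087").

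Section V (Table 5) compares length, width, depth, AMT and RMT between the groups and reports: "There was statistical significant increase in group I than group II regarding length and width (P=0.010, 0.046"). The footnote reads "t-test = student t-test p was significant if", followed by the 0.05 threshold. It does not say whether the tests are one- or two-sided. The table gives no n, and the text does not say that only women with a niche are included.

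In the protocol, niche incidence heads the Outcome measures list. An arm comparison of niche length or width is not on it. The Results section of the protocol promises only standard statistical methods, with no analysis population and no sidedness.

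**The concern.** There are two separate faults.

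**Selection.** Whether a woman has a niche is determined after randomisation and is the outcome the trial set out to compare. If dissection produces some extra niches, the group I subset includes women who would have had none in group II. A difference in mean size between the two subsets then mixes any effect on size with a difference in who was selected. The text gives no warning of this.

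**P values.** If the printed values are not two-sided, the claim of significance for width may rest only on how the test was reported.

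What is at stake is the message. Incidence is reported as non-significant, so length and width are the niche findings a reader is likely to take away as evidence against dissection.

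**Working it through.** **1. Which women are in Table 5.** The depth ranges start at 0.21 cm (group I) and 0.20 cm (group II), and a niche needs at least 0.2 cm. No woman without a niche can be included. Table 4 gives 35 and 26 women with a niche.

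**2. Reproducing the printed P values.** Inputs are the Table 5 means and SDs with n1=35 and n2=26. Pooled test: t = (m1 - m2) / [sp √(1/n1 + 1/n2)], where sp² = [(n1-1)s1² + (n2-1)s2²]/(n1+n2-2), on 59 df.

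- Length: sp² = (34×0.0529 + 25×0.0441)/59 = 0.0492, SE = 0.0574, t = 0.137/0.0574 = 2.39.
- Width: sp² = (34×0.0676 + 25×0.0361)/59 = 0.0543, SE = 0.0603, t = 0.097/0.0603 = 1.61.

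| Measure | Printed P | Two-sided pooled | One-sided pooled |
|---|---|---|---|
| Length | 0.010 | 0.020 | 0.010 |
| Width | 0.046 | 0.113 | 0.057 |
| Depth | 0.421 | 0.674 | 0.337 |
| AMT | 0.441 | 0.879 | 0.440 |
| RMT | 0.378 | 0.758 | 0.379 |

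Length, AMT and RMT match the one-sided column at 35 v 26, which also confirms the subset. Width and depth match neither column. For width, Welch's test gives 0.098 two-sided and 0.049 one-sided, still not 0.046. Rounding in the printed means and SDs moves the two-sided width P only between 0.087 (lowest Welch) and 0.124 (highest pooled).

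Table 4 shows the same halving. Uncorrected chi-square on 35/89 v 26/99 is 1.86, P=0.173, and half of that is the printed 0.087.

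**3. Intervals within the subset.** Difference ± 2.00×SE, pooled:

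- Length: 0.137 cm, 95% CI 0.022 to 0.252.
- Width: 0.097 cm, 95% CI -0.024 to 0.218.

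**4. All women by randomised arm, no niche scored 0 (an assumption).** With k women with a niche out of N: mean M = k·m/N and SS = (k-1)s² + k·m² - N·M². Table 4 accounts for 35+89=124 women in group I and 26+99=125 in group II. Its percentages use 125 in both arms, so one group I woman is missing.

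- Length: 35×0.707/124 = 0.200 v 26×0.570/125 = 0.119 cm. Difference 0.081 (95% CI 0.006 to 0.156), t=2.13, two-sided P=0.034.
- Width: 35×0.737/124 = 0.208 v 26×0.640/125 = 0.133 cm. Difference 0.075 (95% CI -0.005 to 0.155), t=1.85, two-sided P=0.066.

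If the missing woman is counted without a niche, P is 0.037 for length and 0.071 for width. If she is counted with one (36/125), P is 0.026 and 0.053.

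Rank tests need individual data. On 1,000 simulated normal data sets matched to the stated means and SDs, the median two-sided P across the three denominators was about 0.07 to 0.10 for length and 0.09 to 0.12 for width.

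**5. What the all-women difference consists of.** The frequency part is (p1-p2) × the average of the two means, with p1-p2 = 0.282-0.208 = 0.074.

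- Length: 0.0743×0.6385 = 0.047 of 0.081 cm, about 59%.
- Width: 0.0743×0.6885 = 0.051 of 0.075 cm, about 68%.

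**The case against.** Section V is headed as niche characteristics and the preceding table gives 35 and 26, so an attentive reader can work out the subset. That makes the missing denominators a labelling fault. It does not excuse the wording, which presents a selected comparison as a difference between the groups.

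The extent of selection is also uncertain. Incidence differs by about 7 percentage points with two-sided P=0.173, so the subsets may be nearly comparable. This is fair, and the size of any selection bias cannot be established from the documents. But non-significance does not show that the subsets are comparable.

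Three stronger readings are tempting and are not supported:

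- A reader might infer that width loses significance because the analysis moves from the niche subset to all women. The reverse is true: two-sided pooled P falls from 0.113 to 0.066. Setting the printed 0.046 against 0.066 would compare a figure close to a one-sided value with a two-sided one. On one side, like for like, width goes from 0.057 to 0.033. The claim fails because 0.046 does not reproduce and the two-sided value exceeds 0.05 already within the subset.
- A reader might infer that the length difference is spurious. The subset interval excludes zero and the all-women t-test stays below 0.05, while the simulated rank tests do not. The result depends on the method, which is not the same as refuted.
- A reader might infer that these are the only significant comparisons of the whole arms. Table 5 does not compare whole arms, and Table 3 stars a whole-arm difference in uterine position (P=0.03).

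**Conclusion.** The point holds in two parts. First, Table 5 is conditioned on a post-randomisation outcome and is reported as an arm difference without denominators or caveat. This applies to length as much as to width, whatever the sidedness. Second, the printed P values do not agree with two-sided Student t-tests. Width is not significant in the document's own subset (0.113 pooled, 0.098 Welch). Length is 0.020 rather than 0.010.

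The all-women analysis is supporting evidence only. Two-sided width P stays above 0.05 under every denominator tried (0.053 to 0.071). Length is below 0.05 by t-test (0.026 to 0.037) but not by simulated rank test (about 0.07 to 0.10).

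This rests on n=35 and 26, on the means and SDs as printed, on two-sided testing as the norm where no side is stated and, for the all-women figures, on scoring no niche as 0. The Table 4 counts do not depend on Table 5, so the point affects the claims about niche size and not the incidence comparison.

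**What to change.** In Section V and Table 5:

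- Delete the statement that width is significantly greater in group I.
- Print n=35 and n=26, and label the table as descriptive among women with a niche.
- Replace the P values with mean differences and two-sided 95% CIs recomputed from the individual data.
- Do not present the length difference as an effect of the randomised arm.
- State the sidedness of every test, and account for the one group I woman missing from Table 4.

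As a supportive analysis, compare length and width in all scanned women by randomised arm with no niche scored 0. Choose one two-sided test and name it, since the length result depends on that choice.

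The cost is a short re-analysis of existing data and revised text. The downside must be stated alongside it: the all-women measure mixes niche frequency with niche size and mostly reflects frequency here, and the zero score is an assumption because indentations under 2 mm are not reported.
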